## 2.3. Study Design

This study is a Phase 1, open-label, fixed-sequence, 8-period study to evaluate the effect of *PF-07081532* administration on the SD pharmacokinetics of total dabigatran and rosuvastatin in otherwise healthy overweight or obese adult participants. The 8 periods will be conducted sequentially without any washout days between periods.

All participants will provide informed consent and undergo Screening evaluations to determine their eligibility. Screening will occur within 28 days of the first dose of study intervention on Day 1 of Period 1. Participants who discontinue from the study before completing all assessments may be replaced at the discretion of the investigator and sponsor.

Approximately 24 participants will be enrolled such that approximately 16 evaluable participants complete the study.

#### Figure 1. Study Design

The total duration of participation from the Screening Visit to the F/U outpatient telephone contact will be approximately 115 days or 16.5 weeks, approximately 8 weeks of which will be conducted on an inpatient basis.

The 54-day inpatient portion of the study will be conducted as follows:

Period 1: 3 days, includes CRU admission on Day -1 (DE 150 mg single dose);

Period 2: 4 days (rosuvastatin 10 mg single dose);

Period 3: 8 days (PF-07081532 titrated to 40 mg QD);

*Period 4: 5 days (DE 150 mg single dose + PF-07081532 80 mg QD);* 

Period 5: 4 days (rosuvastatin 10 mg single dose + PF-07081532 80 mg QD);

*Period 6: 20 days (PF-07081532 titrated to 240 mg QD);* 

*Period 7: 5 days (DE 150 mg single dose + PF-07081532 240 mg QD);* 

Period 8: 5 days, includes discharge day from CRU (rosuvastatin 10 mg single dose + PF-07081532 240 mg QD).

DMB02-GSOP-RF02 7.0 Statistical Analysis Plan Template 31-Jan-2022 PFIZER CONFIDENTIAL TMF Doc ID: 98.03 Page 8 of 30 The onsite F/U visit/telephone F/U contact will occur 7-10 days from the last dose of study intervention (Period 8, Day 4) and an outpatient telephone F/U contact will occur 28-35 days from the last dose of study intervention (Period 8, Day 4).

# **3. ENDPOINTS AND BASELINE VARIABLES: DEFINITIONS AND CONVENTIONS**

Blood samples for PK analysis of total dabigatran, rosuvastatin, and PF-07081532 will be collected according to the Schedule of Activities given in the protocol.

PK parameters and CCI will be calculated (if possible) from the concentrationtime data using standard noncompartmental methods.

#### **3.1. Primary Endpoint(s)**

- Dabigatran (total) plasma PK parameters: AUCinf (if data permit\* otherwise AUClast) in Periods 1, 4, and 7.
- Rosuvastatin plasma PK parameters: AUCinf (if data permit\* otherwise AUClast) in Periods 2, 5, and 8

\*Should it be deemed that too few AUCinf estimates (e.g. less than 16 for a single treatment) are obtained from the evaluable participants, AUClast may be selected as the primary endpoint for CSR reporting. This will be considered for the rosuvastatin and total dabigatran objectives separately.

AUClast will be calculated and reported regardless of whether AUCinf is the primary endpoint for CSR reporting or not. The plasma PK parameters in Table 2 will be determined:

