# Table 2. Summary of primary total dabigatran and rosuvastatin plasma PK parameters to be calculated.

Parameter	Analysis Scale	Dabigatran Etexilate 150mg (Periods 1, 4 and 7)	Rosuvastatin 10mg (Periods 2, 5 and 8)
AUC inf *	ln	A, D	A, D
AUC last	ln	A, D	A, D

\*=if data permits. Abbreviations: A=analyzed using a statistical model; D=displayed with descriptive statistics as outlined in Table 7 in Section 6.1.1; ln=natural-log transformed.

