## 4. ANALYSIS SETS (POPULATIONS FOR ANALYSIS)

Data for all participants will be assessed to determine if participants meet the criteria for inclusion in each analysis population prior to unblinding and releasing the database and classifications will be documented per standard operating procedures.

Participant Analysis Set	Description
Enrolled	"Enrolled" means a participant's, or their legally authorized representative's, agreement to participate in a clinical study following completion of the informed consent process and assignment to study intervention. A participant will be considered enrolled if the informed consent is not withdrawn prior to participating in any study activity after screening. Potential participants who are screened for the purpose of determining eligibility for the study, but do not participate in the study, are not considered enrolled, unless otherwise specified by the protocol.
Evaluable	All participants assigned to study intervention and who take at least 1 dose of study intervention.
Safety analysis set	All participants randomly assigned to study intervention and who take at least 1 dose of study intervention.
PK Concentration Set	The PK concentration population is defined as all participants who receive at least 1 dose of rosuvastatin, dabigatran etexilate, and/or PF-07081532 and in whom at least 1 plasma concentration value is reported
PK Parameter Set	The PK parameter analysis population is defined as all participants who receive at least 1 dose of rosuvastatin, dabigatran etexilate, and/or PF-07081532 and have at least 1 of the PK parameters of interest calculated. Should vomiting occur after co-administration of rosuvastatin or dabigatran etexilate with PF-07081532, the resulting PK parameters from that participant from the corresponding period may be excluded, where further details are provided in Section 5.3.

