#### 5.3. Methods to Manage Missing Data

For the analysis of safety endpoints, the sponsor data standard rules for imputation will be applied.

In all exploratory safety data presentations (except listings), concentrations below the limit of quantification (BLQ) will be set to the lower limit of quantification (LLOQ).

In all PK data presentations (except listings), concentrations below the limit of quantification (BLQ) will be set to zero. In listings BLQ values will be reported as "<LLOQ", where LLOQ will be replaced with the value for the LLOQ.

In PK summary tables and plots of median profiles, statistics will be calculated having set concentrations to missing if one of the following cases is true:

1. A concentration has been collected as ND (i.e. not done) or NS (i.e. no sample),

2. A deviation in sampling time is of sufficient concern or a concentration has been flagged anomalous by the pharmacokineticist/statistician.

Note that summary statistics will not be presented at a particular time point if more than 50% of the data are missing.

Participants who experience events that may affect their PK profile (e.g., lack of compliance with dosing or vomiting) may be excluded from the PK analysis. At the discretion of the pharmacokineticist a concentration value may also be excluded if the deviation in sampling time is of sufficient concern or if the concentration is anomalous for any other reason.

A full list of protocol deviations will be compiled and reviewed to identify major and minor deviations prior to database closure.

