#### 5.3.1. Plasma Pharmacokinetic Parameters

Actual PK sampling times will be used in the derivation of plasma PK parameters.

DMB02-GSOP-RF02 7.0 Statistical Analysis Plan Template 31-Jan-2022 PFIZER CONFIDENTIAL TMF Doc ID: 98.03 Page 16 of 30 If a PK parameter cannot be derived from a participant's concentration data, the parameter will be coded as NC (i.e., not calculated). (Note that NC values will not be generated beyond the day that a participant discontinues.)

In summary tables, statistics will be calculated by setting NC values to missing; and statistics will be presented for a particular treatment group/analyte with  $\geq$ 3 evaluable measurements. For statistical analyses (i.e., mixed effects model), PK parameters coded as NC will also be set to missing; and analyses will not be performed for a particular parameter if more than 50% of the data are NC.

If an individual participant has a known biased estimate of a plasma PK parameter (due, for example, to an unexpected event such as vomiting before all the compound is adequately absorbed in the body, e.g., within 2 times the median  $T_{max}$  after the last dose for the respective treatment), this will be footnoted in summary tables and will not be included in the calculation of summary statistics or statistical analyses.

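### Does it matter that the SAP sets no time for choosing AUClast over AUCinf as the primary endpoint, and that dropout alone could bring the count below 16?

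*SAP*

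**What the plan says.** SAP Sections 2.2 and 3.1, like the footnotes in Protocol Sections 1.1 and 3, name AUCinf as the primary parameter where the data allow it and AUClast otherwise. The choice is made separately for dabigatran and rosuvastatin. The footnote is permissive and gives an example, "e.g. less than 16 for a single treatment) are obtained from the evaluable participants". Section 3.1 adds that AUClast "will be calculated and reported regardless of whether" AUCinf is primary. SAP Table 2 marks both parameters for modelling and for descriptive display, with AUCinf conditional ("if data permits. Abbreviations: A=analyzed using a statistical model").

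Other data-dependent decisions carry a time. Section 4 has participants assessed "for inclusion in each analysis population prior to unblinding and releasing the database". Section 5.3 states: "A full list of protocol deviations will be compiled and reviewed to identify major and minor deviations prior to database closure". The AUC choice has no such statement.

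Section 4 defines the Evaluable set as "All participants assigned to study intervention and who take at least 1 dose of study intervention". Section 5.3.1 says that "NC values will not be generated beyond the day that a participant discontinues", and that "analyses will not be performed for a particular parameter if more than 50% of the data are NC". Protocol Section 9.5 plans about 24 enrolled so that about 16 evaluable participants complete. Protocol Section 9.1 and SAP Section 5.1 exclude hypothesis testing.

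**The concern.** Two features invite the objection.

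First, the primary label can be settled after the treatment ratios are known. The study is open-label, and Protocol Section 9.4 and SAP Section 7.1 allow the sponsor to review PK data while it runs. A reader of the report could not tell from the plan whether AUClast became primary because AUCinf was poorly estimated or because its ratio looked better.

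Second, the example count does not separate two ways of losing an AUCinf value. One is a profile whose terminal phase cannot be estimated, where AUClast recovers the participant. The other is a participant with no profile at all, where it does not. Since Evaluable in SAP Section 4 needs only one dose, someone who left before Period 7 or 8 stays in the set and supplies no AUCinf. The example equals the planned number of completers, so there is no slack.

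A third point seems to add to this. Section 3.1 illustrates too few estimates with 16, while Section 5.3.1 stops the model only above 50% not calculated. The plan might then seem unclear on whether AUCinf is analysed at all when 12 to 15 values exist.

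At stake would be trust in the headline measure of the interaction for each substrate.

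**Working it through.** **Inputs.** 24 enrolled and 16 evaluable completers (Protocol 9.5); example count below 16 (SAP 3.1); 50% NC rule (SAP 5.3.1); three treatments per substrate with participant as a random effect (SAP 5.2.3). The SDs and CI widths in Protocol Table 13 are redacted, so widths below are in units of the within-participant SD, and the planned widths cannot be reproduced. No dropout rate is given. The planned numbers imply an allowance of 8/24 = 33.3%, and 24 × (1 − 1/3) = 16.

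**1. Can dropout alone meet the example?** With independent dropout at rate d, P = P(X ≤ 15), X ~ Binomial(24, 1 − d). The rates are assumptions.

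| d | 24 participants, none replaced | 28 in total (4 replacements) |
|---|---|---|
| 15% | 0.006 | – |
| 20% | 0.036 | – |
| 25% | 0.121 | 0.011 |
| 30% | 0.275 | 0.049 |

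So it can. The chance is small to moderate, and the replacement allowed by SAP 2.3 cuts it sharply. SAP version 2 records that enough participants reached 240 mg QD, without giving a count.

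**2. What would relabelling do in that case?** The 90% CI half-width on the log scale is t(0.95, df) × √v × SD. With n participants contributing all three treatments and m lacking only the test treatment in question, using within-participant information only:

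- v = (2n + 1.5m) / [n(n + m)], and df = 2n + m − 2.
- n = 16, m = 8: v = 44/384 = 0.1146, df = 38, half-width 1.686 × 0.3385 = 0.571.
- n = 15, m = 9: v = 43.5/360 = 0.1208, df = 37, half-width 1.687 × 0.3476 = 0.586.
- Ratio 0.586/0.571 = 1.03.

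Participants who leave before the substrate dose have neither AUC, so AUCinf and AUClast both rest on the same 15 people. The switch changes precision by 0%.

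**3. What does it do when the terminal phase fails?** With AUClast available on all 24: n = 24, m = 0, v = 2/24 = 0.0833, df = 46, half-width 1.679 × 0.2887 = 0.485.

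- 8 of 24 without AUCinf leaves 16, which does not meet the example: 0.571/0.485 = 1.18.
- 9 of 24 without AUCinf leaves 15, which does: 0.586/0.485 = 1.21.

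Here AUClast is the more precise measure, which is what the fallback is for. The planned model also uses between-participant information, so 18% and 21% are upper bounds.

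**4. Do Sections 3.1 and 5.3.1 conflict?** Take 24 profiles in a treatment and count NC per treatment (an assumption).

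| AUCinf values | NC | Example in 3.1 met? | Model run under 5.3.1? |
|---|---|---|---|
| 16 | 8/24 = 33.3% | no | yes |
| 15 | 9/24 = 37.5% | yes | yes |
| 12 | 12/24 = 50.0% | yes | yes |
| 11 | 13/24 = 54.2% | yes | no |

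Section 3.1 decides which AUC carries the primary label. Section 5.3.1 decides whether a model is fitted. Both can apply at 12 to 15 values: the label may move, and both ratios are still estimated. At 11 or fewer only AUClast is modelled, so there is no choice left to steer.

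**5. Is the reason for switching really open?** Protocol Table 10 attaches the data-permitting condition to AUCinf, half-life, CL/F and Vz/F, the parameters that need the terminal rate constant, and not to AUClast or Cmax. SAP 5.3.1 separates a value that cannot be derived from one that does not exist because the participant has left. Protocol 9.5 and SAP 2.3 use evaluable in the sense of participants who complete. In that setting the footnote concerns estimability. SAP 6.1.1 lists, by treatment, the rate constant, the fit, the extrapolated percentage and the points used, so the report's author has the grounds for the choice in hand.

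**The case for a change.** The strongest case for a change is that it would cost one SAP sentence. The SAP already dates its population and deviation decisions, and the AUC choice depends on the data just as much. Finalising the SAP before analysis, as Protocol 9.3 requires, fixes the document but not a choice the document leaves open. The one-dose definition of Evaluable, read literally, does let dropout meet the example. Even on the completer reading, 15 completers give at most 15 estimates.

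The facts in this stand: no time is given, and the count does not distinguish the two kinds of loss. The inference does not. Relabelling because of dropout would require the sponsor to use a discretionary permission where it brings no benefit, and the reader would still see both ratios. A date tied to the running of the model would protect little when PK data may be reviewed throughout an open-label study. It would also set no criterion for which AUCinf values count as estimable, so the discretion would move rather than disappear.

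One limit applies to the zero-gain result: a participant who leaves during sampling (to 48 hours for dabigatran, 96 hours for rosuvastatin) may have a truncated AUClast and no AUCinf. The zero is exact only for those who leave before the substrate dose or whose values are left out after failed titration.

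**Conclusion.** No change is called for. The plan leaves a detail unstated, but following it as written gives sound results. AUClast is modelled and reported whichever AUC is primary; AUCinf goes through the same model unless more than half its values are not calculated; there is no test, error rate or decision rule for a late choice to distort. Only the label can move, and the listed terminal-phase statistics let the report explain why. In the dropout case relabelling changes precision by 0%, against a loss of about 3% that both AUCs share. In the estimability case the fallback removes a widening of up to about 21% at 15 of 24 values.

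This rests on three readings: that 5.3.1 governs whether AUCinf is modelled, that its percentage is taken per treatment, and that the footnote concerns profiles whose terminal phase cannot be estimated. The dropout probabilities are illustrations at assumed rates. The conclusion does not depend on them, because the consequence is nil whatever the rate.

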# Table 2. Summary of primary total dabigatran and rosuvastatin plasma PK parameters to be calculated.

Parameter	Analysis Scale	Dabigatran Etexilate 150mg (Periods 1, 4 and 7)	Rosuvastatin 10mg (Periods 2, 5 and 8)
AUC inf *	ln	A, D	A, D
AUC last	ln	A, D	A, D

\*=if data permits. Abbreviations: A=analyzed using a statistical model; D=displayed with descriptive statistics as outlined in Table 7 in Section 6.1.1; ln=natural-log transformed.

#### 3.2. Secondary Endpoint(s)

#### 3.2.1. Safety Endpoints

• Assessment of treatment-emergent adverse events (*TEAEs*), clinical laboratory abnormalities, vital signs, body weight, and ECG parameters during the entire study, by period.

DMB02-GSOP-RF02 7.0 Statistical Analysis Plan Template 31-Jan-2022 PFIZER CONFIDENTIAL TMF Doc ID: 98.03 Page 9 of 30 Any events occurring following start of study intervention (i.e. treatment) will be counted as treatment emergent.

Events that occur in a non-treatment period (for example, Washout or Follow-up) will be counted as treatment emergent and attributed to the most recent treatment taken.

A 3-tier approach for summarizing adverse events (AEs) will not be used due to the low number of participants planned to be recruited.

The following data are considered in standard safety summaries (see protocol for collection days and list of parameters):

- adverse events,
- laboratory data (except data from screening visit),
- vital signs data,
- body weight
- ECG results.

For laboratory, vital signs, ECG data, laboratory data and body weight, baseline is defined as the last pre-dose measurement in Period 1.

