# Table 2. Overall Schedule of Activities Period 6 to ET

Visit Identifier Abbreviations used in this table may be found in Appendix 9			riod 6 81532 only	·)	Perio (PF-0708 DF	81532 +	(PF-07	riod 8 7081532 + OSU)	F/U Visit q	F/U Contact Telephone	ET
Day in Study Period a	1-5	6-10	11-15	16-20	1-4	5	1-4	5	7-10	28-35	-
Days in Study b	24-28	29-33	34-38	39-43	44-47	48	49-52	53 f	59-62	80-87	-

- c. Brief exam if findings during previous exam or new/open AEs, if appropriate, at investigator discretion.
- d. Participants will be screened for COVID-19 according to local practice prior to being admitted to the clinic for confinement in Period 1. A subsequent test will be done according to local procedure if participants develop COVID-19 like symptoms. See also Section 8.3.5 (COVID-19 Specific Assessments). If participants test positive for SARS-CoV-2 infection, they will be discharged from the study.
- e. C-SSRS and PHQ-9 will be administered in Period 6 on Days 5 and 19, and in Period 8 on Day 5 (discharge from CRU).
- f. Discharge from CRU.
- g. Body weight to be obtained on Days 5, 12 and 19 in Period 6.
- h. ECG to be obtained on Day 10 of Period 6.
- i. Assessments to be obtained on Day 5 of Period 8 prior to D/C from the CRU.
- j. Includes BP and PR predose; to be obtained on Days 5, 12 and 19 in Period 6.
- k. Collection following fasting duration specified in Section 5.3.2.
- 1. Chemistry to be obtained on Days 1 and 20 in Period 6; calcitonin, amylase, lipase and hematology to be obtained on Day 20 in Period 6.
- m. Serum β-hCG for all WOCBP
- n. Dosing to occur QD with breakfast. Note that there is no PF-07081532 administration on Study Day 53 or anytime thereafter.
- o. The rosuvastatin PK sample is to be collected predose (0 hr) on Day 1 of Period 6.
- p. Participants may undergo random urine drug testing at the discretion of the investigator.
- q. The follow-up visit 7-10 days after the last dose of study intervention (Period 8, Day 4) can be on-site or via telephone call. Whether the follow-up visit is on-site or via telephone call is at the discretion of the Investigator. Regardless of location (ie, on site or telephone call), contraception use, drug, alcohol/tobacco use, concomitant medications and AEs must be reviewed/assessed as appropriate.

Table 3. Schedule of Activities – Period 1 (DE ONLY), Period 4 (DE + PF-07081532 80 mg QD) and Period 7 (DE + PF-07081532 260 mg QD)

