# 4. STUDY DESIGN

# 4.1. Overall Design

This is a Phase 1, open-label, fixed-sequence, 8-period study to evaluate the effect of PF-07081532 administration on the SD pharmacokinetics of dabigatran (total) and

\* Should it be deemed that too few AUCinf estimates (eg, less than 16 for a single treatment) are obtained from the evaluable participants, AUClast may be selected as the primary endpoint for CSR reporting. This will be considered for the rosuvastatin and dabigatran objectives separately.

rosuvastatin in otherwise healthy overweight or obese adult participants. The 8 periods will be conducted sequentially without any washout days between periods.

All participants will provide informed consent and undergo Screening evaluations to determine their eligibility. Screening will occur within 28 days of the first dose of study intervention on Day 1 of Period 1. Participants who discontinue from the study before completing all assessments may be replaced at the discretion of the investigator and sponsor.

Approximately 24 participants will be enrolled.

The total duration of participation from the Screening Visit to the F/U outpatient telephone contact will be approximately 115 days or 16.5 weeks, approximately 8 weeks of which will be conducted on an inpatient basis.

The 54-day inpatient portion of the study will be conducted as follows:

Period 1: 3 days, includes CRU admission on Day -1 (DE 150 mg single dose);

Period 2: 4 days (rosuvastatin 10 mg single dose);

Period 3: 8 days (PF-07081532 titrated to 40 mg QD);

Period 4: 5 days (DE 150 mg single dose + PF-07081532 80 mg QD);

Period 5: 4 days (rosuvastatin 10 mg single dose + PF-07081532 80 mg QD);

Period 6: 20 days (PF-07081532 titrated to 260 mg QD);

Period 7: 5 days (DE 150 mg single dose + PF-07081532 260 mg QD);

Period 8: 5 days, includes discharge day from CRU (rosuvastatin 10 mg single dose + PF-07081532 260 mg QD).

The onsite F/U visit/telephone F/U contact will occur 7-10 days from the last dose of study intervention (Period 8, Day 4) and an outpatient telephone F/U contact will occur 28-35 days from the last dose of study intervention (Period 8, Day 4).

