Period 8, Days 1-5*	49-53*	PF-07081532 260 mg QD + SD Rosuvastatin 10 mg

\*No drug administration in Period 8, Day 5 (Study Day 53); participants discharged from the CRU.

Modification of PF-07081532 dosing may be permitted **upon sponsor approval only** (see Section 6.6).

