## **5. GENERAL METHODOLOGY AND CONVENTIONS**

#### 5.1. Hypotheses and Decision Rules

There is no statistical hypothesis testing planned for this study and no statistical decision rules will be applied.

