#### 5.2. General Methods

Unless otherwise stated, all summaries and plots will be presented by treatment group (equivalent to 'by Period'). The following treatment labels (or similar) will be used, which represent Periods 1 to 8 as:

Period	Treatment Label
1	Dabigatran etexilate 150 mg (Period 1)
2	Rosuvastatin 10 mg (Period 2)
3	PF-07081532 titration up to 40 mg QD (Period 3)
4	PF-07081532 80 mg QD + dabigatran etexilate 150 mg (Period 4)
5	PF-07081532 80 mg QD + rosuvastatin 10 mg (Period 5)
6	PF-07081532 titration up to 240 mg QD (Period 6)
7	PF-07081532 240 mg QD + dabigatran etexilate 150 mg (Period 7)
8	PF-07081532 240 mg QD + rosuvastatin 10 mg (Period 8)

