#### 6.2. Secondary Endpoint(s)

#### 6.2.1. Safety Endpoints

#### 6.2.1.1. Adverse Events

Adverse events will be summarized by treatment and overall and in accordance with sponsor reporting standards using the safety population defined in Section 4.

Incidence and severity of treatment emergent adverse event (TEAE) tables will additionally be produced ('All causality' and 'Treatment related', separately) to summarize the total number of adverse events by preferred term, which will be reported by treatment and overall in accordance with sponsor reporting standards using the safety analysis set defined in Section 4.

The AEs will be presented sorted in descending frequency based on the overall number of AEs (by preferred term or system order class as appropriate) across treatments.

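### SAP 3.2.1 tabulates completers' follow-up adverse events under Period 8 (240 mg QD + rosuvastatin), so that column spans about 32-39 days against 4 for Periods 2 and 5; follow-up onset should be shown separately

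*SAP*

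**What the plan says.** SAP 3.2.1 treats every event after the start of study intervention as treatment emergent and sets no end to that window. Events in a "non-treatment period (for example, Washout or Follow-up) will be counted as treatment emergent and attributed to the most recent treatment taken". SAP 5.2 makes treatment group the same thing as period and gives eight labels. The eighth is "PF-07081532 240 mg QD + rosuvastatin 10 mg (Period 8"), and there is none for follow-up. SAP 2.3 has no washout between periods, so follow-up is the only non-treatment interval that a completer has.

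SAP 6.2.1.1 summarises adverse events by treatment and overall, under sponsor reporting standards that are not part of the documents. Incidence and severity "tables will additionally be produced ('All causality' and 'Treatment related', separately) to summarize the total number of adverse events by preferred term". SAP 6.5.3, on exposure, is marked not applicable. Nothing in the SAP text separates follow-up onset or states how long each column's window is. SAP 5.1 adds: "There is no statistical hypothesis testing planned for this study and no statistical decision rules will be applied".

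The schedule comes from these places:
- SAP 2.3: "Period 5: 4 days (rosuvastatin 10 mg single dose + PF-07081532 80 mg QD"). Period 2 also lasts 4 days.
- Protocol Table 8, footnote: "No drug administration in Period 8, Day 5 (Study Day 53); participants discharged from the CRU".
- Protocol 4.1: "an outpatient telephone F/U contact will occur 28-35 days from the last dose of study intervention (Period 8, Day 4").
- Protocol Table 2 has one earlier contact, 7-10 days after the last dose: "Whether the follow-up visit is on-site or via telephone call is at the discretion of the Investigator".
- SAP 2.1 reports that dosing was capped at 240 mg QD and the study shortened by 6 days. It does not say which days were removed.

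**The concern.** One secondary objective is the safety of PF-07081532 alone and together with rosuvastatin, and SAP 3.2.1 assesses treatment-emergent events by period. The by-treatment tables are therefore the display that serves this objective, and Period 8 is its highest-dose combination column.

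Two kinds of observation are merged under that label. One is a few inpatient days on both drugs. The other is about four to five weeks after the last dose, with two scheduled contacts. Periods 2 and 5, the other rosuvastatin columns, hold inpatient days only. A reader of the table cannot tell how many Period 8 events arose during coadministration and how many arose weeks later. At stake is the interpretation of one column in a descriptive safety table.

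**Working it through.** **1. Reproduce the plan's durations.** Inpatient: 3 + 4 + 8 + 5 + 4 + 20 + 5 + 5 = 54 days, as stated. Total: 28 screening days + Study Day 87 = 115 days, as stated.

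**2. Window of each column** (Study Days from Protocol Tables 1, 2 and 8):

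| Column | Study Days | Days |
|---|---|---|
| Period 1 | 1-2 | 2 |
| Period 2 (rosuvastatin) | 3-6 | 4 |
| Period 3 | 7-14 | 8 |
| Period 4 | 15-19 | 5 |
| Period 5 (rosuvastatin) | 20-23 | 4 |
| Period 6 | 24-43 | 20 |
| Period 7 | 44-48 | 5 |
| Period 8 through discharge (rosuvastatin) | 49-53 | 5 |
| Period 8 as tabulated for a completer | 49 to 80-87 | 32-39 |

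The last dose is on Day 52, so the final contact falls on Day 52 + 28 = 80 to 52 + 35 = 87. The window is 80 - 49 + 1 = 32 days to 87 - 49 + 1 = 39 days.

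**3. Share after the last dose.** 28/32 = 87.5% to 35/39 = 89.7%. Split at discharge, the column holds 5 in-period days and 27-34 follow-up days.

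**4. How much of that time drug is likely to be present.** The longest mean half-life that Protocol 2.2.4.1 reports for PF-07081532 is 26.50 h. Five half-lives are 132.5 h, about 5.5 days after the last dose. That leaves 28 - 5.5 = 22.5 to 35 - 5.5 = 29.5 later days. Rosuvastatin's half-life is about 19 h (Protocol 4.3). Five half-lives are 95 h, about 4 days after the Day 49 dose, which is close to discharge.

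**5. Effect of the 6-day shortening.** Study Day numbers may move. The window length does not, if Period 8 kept 4 dosing days, because follow-up is timed from the last dose. SAP 2.3 still lists Period 8 as 5 days including discharge, and rosuvastatin sampling runs to 96 h (Protocol Table 4), which fits. Even with a single dosing day the window would be 1 + 28 = 29 to 1 + 35 = 36 days.

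**6. Effect on incidence.** A participant is counted once per column, or once per preferred term in a term-level row. A follow-up event changes Period 8 incidence only if that participant has no in-period event of that kind. Each such participant adds 1/16 = 6.25 percentage points with the roughly 16 completers planned, or 1/24 = 4.2 points if all 24 enrolled reach Period 8. The documents give no adverse event rate, so the number of such participants cannot be estimated.

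**The case against.** The case against is substantial. The rule is stated openly, agrees with the collection period of at least 28 days in Protocol 8.4.1, and is cautious in that it drops no late event. The tables carry no test, decision rule or planned between-period contrast. The treatment-related tables should leave out follow-up events judged unrelated. The sponsor's table standards are unseen and may already separate follow-up onset. A cut at discharge falls about one day after the last dose, when PF-07081532 is still present. All of this stands. It limits the point to presentation, and the last item calls for a footnote. It does not change the fact that, on the SAP text, the Period 8 label covers mostly time after the last dose without saying so.

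Three stronger readings are tempting and are not supported:
- **That Period 8 incidence is inflated eight- to tenfold.** The ratio of days is 32/4 = 8 to 39/4 = 9.75, but it is not a ratio of events. No event rate is given, and events may be reported less often per day through two contacts than in the unit.
- **That every follow-up event raises Period 8 incidence.** It does so only under the condition in step 6 of the working.
- **That a split would make Periods 2, 5 and 8 comparable.** They would still differ in dose and cumulative exposure, in a fixed sequence without washout, and Period 2 precedes any PF-07081532. Other columns differ in length too, from 2 to 20 days.

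**Conclusion.** The point holds as a minor matter of presentation. For completers, the SAP text gives the Period 8 column a window of about 32-39 days, against 4 inpatient days for Periods 2 and 5. About 88-90% of it lies after the last dose and is observed through two scheduled contacts. The possible distortion is 6.25 points (16 participants) or 4.2 points (24 participants) for each participant whose only Period 8-attributed event, or only event of a given preferred term, starts in follow-up. The total is unknown and may be nil. The overall column and the primary PK analysis are not affected.

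This rests on two assumptions: that Period 8 kept 4 dosing days after the shortening, and that the unseen sponsor tables do not already separate follow-up onset. It is limited to completers. For a participant who stops early, follow-up events go to the last treatment that participant took.

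**What to change.** Keep the treatment-emergent definition, the attribution to the last treatment, the combined count and the overall column. In the by-treatment incidence and severity tables of SAP 6.2.1.1:
- Show events that start in the period separately from events that start in follow-up. The in-period part runs through the Period 8 discharge day or, for discontinuers, to the end of the last period dosed.
- Keep the combined count beside the two parts. A participant with events in both parts is counted in each part and once in the combined count, so the parts need not add up.
- State each column's window length in a footnote. Do not add rates or a participant-days row: setting inpatient days against telephone-contact days would invite a comparison that the design cannot support.
- Add a footnote that events in the first days after the last dose may occur with drug still present.

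If the sponsor's standard tables already separate follow-up onset, one sentence in SAP 6.2.1.1 saying so is enough.

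The cost is one split and a few footnotes, from onset and dosing dates that are already collected, and a small departure from the standard table layout. The risk is that a delayed drug-related event is dismissed because it sits in the follow-up part, which is why the combined count and the footnote should stay.
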